7. DRUG FORMULATION AND ADMINISTRATION

7.1 Pyrimethamine

7.1.1 Description

The chemical name of pyrimethamine is 5-(4-chlorophenyl)- 6-ethyl-2,4-pyrimidinediamine. It acts as a folate antagonist and a STAT3 inhibitor.

Pyrimethamine is well absorbed orally with peak levels occurring between 2 to 6 hours following administration. It is eliminated slowly and has a plasma half-life of approximately 96 hours. Pyrimethamine is 87% bound to human plasma proteins.

7.1.2 Form

Pyrimethamine is supplied as 25 mg tablets. Depending on dose level, 0.5, 1 or 2 tablets will be taken by mouth once per day while on study. Do not crush or chew. *The 25 mg tablet is scored, and will be split in half either by the research nurse or pharmacist.

7.1.3 Storage and Stability

Pyrimethamine is stored at room temperature and protected from light.

7.1.4 Availability

The agent is commercially available, but will be provided free of charge to patients enrolled on this protocol.

7.1.5 Ordering

The agent will be ordered by the Investigational Pharmacy who will maintain adequate stocks for this protocol.

7.1.6 Accountability

The investigator, or a responsible party designated by the investigator, must maintain a careful record of the inventory and disposition of the agent using the NCI Drug Accountability Record Form (DARF) or another comparable drug accountability form. (See the CTEP home page at <http://ctep.cancer.gov> for the Procedures for Drug Accountability and Storage or to obtain a copy of the DARF.)

7.1.7 Destruction and Return

Study drug for daily oral administration will be supplied by the DFCI pharmacy as 25 mg tablets in bottles. Drug accountability will be performed as per current DF/HCC SOP All unused study drug should be returned by the patient to the Investigator or research nurse/PA.

At the end of the study, unused supplies of pyrimethamine should be destroyed according to institutional policies. Destruction will be documented in the Drug Accountability Record Form.

8. CORRELATIVE/SPECIAL STUDIES

8.1 Pharmacokinetic Studies

Pharmacokinetics will be performed to assess pyrimethamine accumulation over time, given the long half-life of the drug. 1 heparin-anticoagulated green top tube will be drawn prior to therapy, prior to dose on **one** of days 2-5 (optional) and prior to dose on each subsequent clinic visit (weekly during cycle 1, every other week during cycle 2, and monthly thereafter until discontinuation from study drug. Pharmacokinetics will also be drawn at time of off study visit and once again 2-4 weeks later if the patient has

not started additional therapy. These samples will be collected at all of the above timepoints and transferred for processing and freezing.

PK samples are drawn, processed and stored as follows:

The [name] Laboratory – a division of
Louis B. Mayer Research Laboratories
[name], Laboratory Director
[name]
Dana-Farber Cancer Institute
[name]
[name]

The frozen samples will be processed in batches by the DF/HCC Core Pharmacokinetics laboratory run by [name]:

Clinical Pharmacology Lab
[name], Director
Gray / Jackson
Massachusetts General Hospital
[name]
[name]

8.2 Pharmacodynamic Studies

Pharmacodynamic studies will be run in [name] lab.

Two 6 cc heparin-anticoagulated green top tubes (or equivalent) will be collected and transferred to [name] lab on Mayer 5 on the following days/times:

- Screening
- Pre and two hours post drug on day 1 of cycle 1
- One day among Days 2-5 therapy (optional)
- Day 8, 15, 22 cycle 1
- Day 1 and 15 cycle 2
- Day 1 of subsequent cycles up to cycle 6
- Off study visit
- 2-4 weeks after off study visit (if subsequent therapy has not begun)
- 3 month follow up appointment (if subsequent therapy has not begun)

As outlined above, prior to initiating therapy, and at the time of each subsequent clinic visit while on study, patients will have approximately 10 ml of blood drawn into a heparinized tube. Mononuclear cells will be isolated by Ficoll-based density separation, and the proportion of CLL cells will be determined by flow cytometry. If greater than 90% of the isolated cells are CLL cells (CD5+CD19+CD20+), these will be used for subsequent analyses. If less than 90% display a CLL phenotype, then we will use antibody-based

magnetic cell separation to increase the purity to this level. It will be necessary to isolate a minimum of 5×10^6 cells for the required analyses.

Cells will be analyzed in two ways in parallel, as follows.

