1.3 Secondary Objectives

- To assess the toxicity profile of pyrimethamine in relapsed CLL/SLL and T-LGL, both acutely and over prolonged daily dosing.
- To determine pyrimethamine levels in vivo with prolonged dosing.
- To determine the progression-free survival following pyrimethamine for the treatment of relapsed CLL/SLL and T-LGL.
- To determine whether pyrimethamine inhibits STAT3 in vivo by assessing downregulation of STAT3 dependent gene expression in CLL cells, and T-LGL and/or peripheral blood mononuclear cells.
- To determine whether known prognostic factors in CLL/SLL and T-LGL correlate with response to pyrimethamine.
- To assess the impact of CT scans on response evaluation in relapsed CLL/SLL and T-LGL.

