14.4 Secondary Objectives

- To assess the toxicity profile of pyrimethamine in relapsed CLL/SLL and T-LGL, both acutely and over prolonged daily dosing.
- To determine pyrimethamine levels in vivo with prolonged dosing.
- To determine the progression free and overall survival following pyrimethamine for the treatment of relapsed CLL/SLL and T-LGL.
- To determine whether pyrimethamine inhibits STAT3 in vivo by assessing downregulation of STAT2 dependent gene expression in CLL cells and/or peripheral blood.
- To determine whether known prognostic factors in CLL/SLL correlate with response to pyrimethamine.
- To assess the impact of CT scans on response evaluation in relapsed CLL/SLL and T-LGL.

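### Section 8.2 gives only a CLL cell gate for the pharmacodynamic samples, so the serial data cannot show STAT3 inhibition in T-LGL cells, and no alternative route is specified

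*Combined protocol and SAP*

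**What the plan says.** The secondary objective in section 1.3 is to assess "downregulation of STAT3 dependent gene expression in CLL cells, and T-LGL and/or peripheral blood mononuclear cells". Section 14.4 restates it as "STAT2 dependent gene expression in CLL cells and/or peripheral blood", which leaves out T-LGL cells and names STAT2.

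Section 8.2 sets the procedure. Mononuclear cells are isolated by density separation, then gated: "If greater than 90% of the isolated cells are CLL cells (CD5+CD19+CD20+), these will be used for subsequent analyses". For the other samples, "If less than 90% display a CLL phenotype, then we will use antibody-based" magnetic separation raises the purity to that level. On yield: "It will be necessary to isolate a minimum of" 5 × 10⁶ cells. The rule is written for patients in general and names no T-LGL phenotype. Footnote 5b of the study calendar (section 9) makes no T-LGL exception for these samples.

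The assay sections, 8.2.1.1 and 8.2.2.1, refer only to CLL cells, and the ten-gene panel was chosen in CLL cells treated in vitro. Section 8.3 separately banks mononuclear cells from all T-LGL patients at screening and day 15, with no CLL sort described and no STAT3 assay attached. Section 14.5 analyses the ratio of post-treatment to baseline expression.

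**The concern.** CD19 and CD20 are B-cell antigens (section 3.1.1 calls them that), and T-LGL is a T-cell leukaemia. A sort to CD5+CD19+CD20+ cells therefore leaves the T-LGL clone behind.

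The protocol adapts to T-LGL in other places: neutropenia as a dose-limiting toxicity (5.3), allopurinol (5.4), CT scans (section 9), banking (8.3) and response criteria (section 10). Section 8.2 was not adapted, although section 2.2 gives STAT mutations as the reason for adding T-LGL.

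Two uses of the data are at stake. Section 5 makes PD results one input to the recommended Phase 2 dose. Section 2.4, writing about CLL, says that if the drug shows no activity it will be essential to know whether STAT3 was inhibited. The same question arises for T-LGL, and samples handled by the stated rule could not answer it.

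**Working it through.** The plan gives no statistical figure on this point to reproduce. The check is a comparison of the texts plus a cell-yield calculation.

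**Inputs from section 8.2.** Minimum N = 5 × 10⁶ cells. Volume V is given in two ways: "patients will have approximately 10 ml of blood drawn into a heparinized tube" (10 ml) and "Two 6 cc heparin-anticoagulated green top tubes (or equivalent) will be collected" (2 × 6 = 12 ml).

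**1. Concentration needed.** c = N / (V × 1,000 × r), where r is the recovered fraction.

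| V | r = 100% | r = 50% (assumed) |
|---|---|---|
| 10 ml | 500 per microliter | 1,000 per microliter |
| 12 ml | 417 per microliter | 833 per microliter |

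**2. Yield from a T-LGL sample under the CLL gate.** The documents give no B-cell counts for T-LGL patients. Assume 50 to 500 B cells per microliter, 10 to 30% of them CD5+, and 50 to 100% recovery.

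- Strict CD5+CD19+CD20+ gate: from 50 × 0.10 × 10 × 1,000 × 0.5 = 0.025 × 10⁶ to 500 × 0.30 × 12 × 1,000 × 1 = 1.8 × 10⁶. This is always below the minimum.
- If the sort takes all B cells (the antibody is not named): from 50 × 10 × 1,000 × 0.5 = 0.25 × 10⁶ to 500 × 12 × 1,000 × 1 = 6.0 × 10⁶. The minimum is reached only near the top of the range with near-complete recovery, and the cells are not the leukaemia.

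**3. Samples affected.** Section 8.2 schedules up to 16 PD draws per patient: screening 1, cycle 1 day 1 before and after dose 2, days 2–5 (optional) 1, days 8, 15 and 22 3, cycle 2 2, cycles 3–6 4, off study 1, and two later visits 2. The same gate applies to all of them.

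**4. Yield without sorting.** Assume 1,000 to 10,000 lymphocytes per microliter and 50 to 100% recovery. The yield runs from 1,000 × 10 × 1,000 × 0.5 = 5 × 10⁶ to 10,000 × 12 × 1,000 × 1 = 120 × 10⁶, so the minimum can be met.

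**5. Why unsorted cells need a rule.** In a mixture, the post/baseline ratio moves when the cell mix moves. As an illustration with assumed values, let LGL cells express a gene at 4 times the level of the other cells, and let their share fall from 60% to 30%. The ratio is (0.3 × 4 + 0.7) / (0.6 × 4 + 0.4) = 1.9 / 2.8 = 0.68, an apparent 32% fall with no change in any cell.

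**6. Why a T-LGL sort needs its own minimum.** Complete response in T-LGL requires a circulating LGL count below 500 per microliter (section 10). At 10 ml and full recovery that is below 500 × 10 × 1,000 = 5 × 10⁶, so every complete responder falls short. At 12 ml, those below 417 per microliter fall short at full recovery, and all do once recovery is at or below 5/6 (83%). Keeping the present minimum would lose data mainly from responders.

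**The case against.** The strongest reply is that the T-LGL objective can still be met. Section 1.3 accepts mononuclear cells, section 8.2 isolates them before any sort, and the cells banked under 8.3 form a pre/post pair that suits the ratio analysis in 14.5. This stands. A reader might infer that the T-LGL part of the objective cannot be answered at all; the documents do not support that. But the banked cells cover only two time points and have no assay assigned, so the route exists without being specified.

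A second reply is that T-LGL was added by amendment and section 8.2 was simply not updated, so it is silent on T-LGL and does not tell the laboratory to discard the clone. That is a fair account of how the gap arose. Still, the rule is worded for all patients, and a laboratory following it would lose the T-LGL cells.

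Third, the number of T-LGL patients in the remaining dose cohorts is not stated and may be small, and CLL patients still supply PD data. This limits the consequence, and nothing here shows that the choice of Phase 2 dose would go wrong.

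**Conclusion.** The point holds as a conflict between sections 1.3 and 8.2. Applied literally, 8.2 yields no information on STAT3 inhibition in T-LGL cells at any scheduled PD draw, and the alternative through mononuclear cells is left undefined. It is a minor point that is cheap to correct.

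The 417 to 500 per microliter threshold follows from the documents' own figures at full recovery. The expected shortfall rests on assumed B-cell counts, CD5+ share and recovery; under those ranges too few cells is the usual outcome and non-leukaemic B cells the exception. The conclusion that neither outcome measures the T-LGL clone does not depend on those assumptions.

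**What to change.** 1. In section 8.2, limit the CLL gate to CLL/SLL patients and add a T-LGL branch: either a sort on a defined T-LGL phenotype with its own minimum cell number, or unsorted mononuclear cells.
2. Where unsorted cells are used, record the LGL fraction at each time point at the flow cytometry step that 8.2 already includes, and interpret the post/baseline ratio alongside it.
3. Report T-LGL PD results separately from CLL, noting that the gene panel was selected in CLL cells. A new sort antibody alone does not establish that the panel is informative in T-LGL.
4. State whether the cells banked under 8.3 will be assayed for STAT3, and align section 14.4 with 1.3 on both the cell populations and the STAT named.

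The cost is a different sort antibody and slightly more laboratory and analysis work, with no extra patients or blood draws. It is best settled before T-LGL samples are processed, since cells removed in a CLL sort may not be recoverable afterwards.

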8.2.1 Laboratory Correlative Studies: Determination of STAT3 Inhibition In Vivo

8.2.1.1 STAT3 Phosphorylation

An aliquot of 1×10^6 cells will be used for a quantitative flow cytometric assay to measure total STAT3 and serine phosphorylation of STAT3. Cells will be fixed, permeabilized, and stained with the specific antibodies, employing a technique we have used successfully on clinical CLL specimens in the past²⁰. This analysis will indicate the concordance of normalized expression of STAT3 target genes (as described below) with the level and phosphorylation of STAT3. In addition, it will allow a longitudinal analysis of changes in the quantity and phosphorylation state of STAT3 in CLL cells of patients on pyrimethamine. If pyrimethamine is decreasing the survival of CLL cells in these patients, then it will be expected that the total number of CLL cells will decline over time. Furthermore, if CLL cells persist, it will allow a determination of whether a change in the proportion of CLL cells with activated STAT3 is occurring over time.

8.2.2.1 STAT3 Target Gene Expression

We will also analyze expression of a panel of 10 STAT3 target genes that we have found to be most informative of pyrimethamine-induced STAT3 inhibition in CLL cells treated in vitro, as well as four genes we have found to be invariant which will be used for normalization. STAT3 target gene expression will be quantitated for individual genes, and a weighted normalized score will also be generated¹². This analysis will provide a correlation of STAT3-dependent gene expression with STAT3 phosphorylation by the flow cytometric assay, a determination of the effect of pyrimethamine dosing on STAT3-dependent gene expression, and a longitudinal analysis of STAT3 dependent gene expression with pyrimethamine treatment in individual patients. Furthermore, in conjunction with the pharmacokinetic analyses described above, these studies will provide correlations between plasma concentrations of pyrimethamine and effects on STAT3 phosphorylation and STAT3-dependent gene expression.

9. STUDY CALENDAR

Baseline evaluations are to be conducted within 1 month prior to start of protocol therapy. CBCD and chemistry blood will be redrawn on Cycle 1 Day 1. Scans must be done ≤ 4 weeks prior to the start of therapy. In the event that the participant's condition is significantly deteriorating, laboratory evaluations should be repeated within 48 hours prior to initiation of the next cycle of therapy.

All assessments must be performed prior to administration of any study medication. Failure to perform any assessment prior to administration of study drug will constitute a protocol violation. The Principal Investigator will determine if the event is a minor or major violation, per DF/HCC SOPs. Informed Consent must take place prior to any study specific procedures. All study assessments and medications should be administered within ± 3 days of the protocol-specified date, unless otherwise noted.

Study Calendar Follows

Test/Procedures	Pre-Study	Weekly in 1st 28 day	Every 2 wks in 2nd cycle	Every 3-6 months at investigator discretion and
------------------------	------------------	--	--	--

		cycle (TLS blood X2 1st week of C1)	and then monthly	at discontinuation of study treatment
Informed Consent	X			
History/PE/AE evaluation/ Perf. status	X	X	X	X
Weight/VS	X	X	X	X
Screen & Replete Folate (replete as necessary)	X		X ¹⁰	
Concomitant Meds	X	X	X	
CBC with Diff [*]	X	X	X	X
CMP ^{1,*}	X	X	X	X
Tumor Lysis Monitoring ^{1A}	X	X		
CAP CT ^{**}	X		X ²	X ²
Tumor Measurement by physical exam ⁹	X		X ⁹	X ⁹
Bone Marrow Biopsy	X			X ⁷
FISH ⁸	X			
Patient Diary	X ⁴	X ⁴	X ⁴	X ⁴
Pharmacokinetic Studies	X ^{5a}	X ^{5a}	X ^{5a}	X ^{5a}
Pharmacodynamic Studies	X ^{5b}	X ^{5b}	X ^{5b}	X ^{5b}
CD4 count (T cell subsets)	X		X ⁶	X ⁶
IgG, IgA, IgM	X		X ⁶	X ⁶
Beta-2-microglobulin	X		X ⁶	X ⁶
Flow cytometry for CD38 ⁸	X			
Samples for CLL prognostic factors/tissue banking ³	X ³	X ³		
IgVH Testing	X			

1 Comprehensive Metabolic Panel: Creatinine, glucose, total bilirubin, alkaline phosphatase, and SGOT/SGPT, LDH. Serum beta-HCG within seven days prior to initiation of therapy for women of child-bearing potential.

1A Investigators should monitor patients for tumor lysis with calcium, magnesium, phosphate, uric acid and LDH, in addition to a full comprehensive metabolic panel, twice during the first week, weekly for the rest of cycle 1, and then subsequently at times of other lab draws for the rest of the study. Treatment for TLS should commence should evidence of such

- be demonstrated. At a minimum, hyperuricemia, hydration, and electrolyte disturbances should be monitored closely and addressed promptly.
- 2 CT scans (chest/abdomen/pelvis) to be performed at screening in all patients and again at the end of the 1st, 3rd and 6th months of therapy; subsequent scans shall be at the discretion of the treating physician if needed for adequate response evaluation.
 - 3 Please see Section 8.3 "Determination of CLL Biologic Prognostic Factors" for details on sample collection.
 - 4 Diary dispensed with study drug and retrieved at scheduled visits.
 - 5a One heparin-anticoagulated green top tube (pharmacokinetic studies) to be collected during screening, on cycle 1 day 1 prior to drug; prior to drug on one day among days 2, 3, 4 or 5, (optional); and prior to dose (trough) at each subsequent clinic visit as per Section 8.1, above. A heparin-anticoagulated green top tube will also be collected at time of off study visit and once again 2-4 weeks later if the patient has not started additional therapy. All samples are to be delivered to the [name] lab on Mayer 5. This includes BIDMC patients.
 - 5b Two 6 cc heparinized blood for cell isolation (pharmacodynamic studies) is to be collected during screening, on cycle 1 day 1 prior to drug and approximately two hours after drug administration, prior to dose (trough) on days 2, 3 4 or 5 of therapy, pre drug on cycle 1 days 8, 15, and 22, cycle 2 days 1 and 15, and day 1 of subsequent cycles monthly up to cycle 6. Pharmacodynamic studies will also be collected at time of off study visit, 2-4 weeks later if the patient has not started additional therapy, and lastly at the 3 month follow up appointment (if subsequent therapy has not started). These are to be delivered to the [name] lab on Mayer 5. This includes BIDMC patients.
 - 6 These laboratory tests will be done at baseline, at the end of cycles 1, 3, 6, end of treatment, and every 3-6 months in follow-up.
 - 7 Bone marrow biopsy will be done at screening (unless done within previous 6 months and the Principal Investigator feels it does not need to be repeated, or if prior marrow was positive and the patient has not had CLL treatment since) and thereafter only to confirm CR. Confirmation of complete response by bone marrow biopsy should occur approximately 3 months after the clinical criteria for CR are first met. Bone marrow biopsy is not required at off study.
 - 8 To be performed on bone marrow if aspirate obtained; otherwise on peripheral blood prior to therapy initiation.
 - 9 Up to 6 palpable nodes should be followed as targets, with bi-dimensions noted by the clinician whenever possible. To be performed at screening in all patients and again at the end of the 1st, 3rd and 6th months of therapy, and in follow up if needed for adequate response evaluation.
 - 10 If deficient at baseline, folate level should be redrawn approximately every month while on study drug, or at required visits, whichever is less.
- * Hematology and chemistry blood tests should be result and patient assessed for toxicity prior to taking dose of pyrimethamine.
- ** Subjects with T-LGL do not require radiology

10. MEASUREMENT OF EFFECT

Responses will be formally assessed initially at the conclusion of the 1st 28 day cycle, then at the conclusion of three cycles (three months), and then every three months thereafter, until disease progression, start of another treatment, or death. Response will be assessed in two ways: (1) By NCI-WG 1996 criteria³ (as updated in the IWCLL 2008 criteria Section 10.2)¹⁹ without the use of CT scans. In this case lymph nodes will be assessed based on physical exam measurements; (2) With the incorporation of CT findings as suggested for clinical trials in IWCLL 2008. Thus CT scans will be performed on all patients at the end of the 1st month, 3rd month and 6th month, if still on study we will evaluate the impact of the CT scans (1) if used only to confirm CR; (2) if used to assess lymphadenopathy regardless of PE findings. After the 6 month evaluation, further CT scans will generally not be done, but may be done at the discretion of the treating physician.

Following the initial screening bone marrow biopsy, additional bone marrow biopsies will be performed only to confirm complete remission.

T-LGL Response Criteria²¹:

Response to treatment should be evaluated by history, physical examination, and complete blood count with differential:

- Complete response — A hematologic complete response is defined as the complete normalization of blood counts (ie, hemoglobin >12 g/dL; platelets >150,000/microL; absolute neutrophil count >1500/microL; absolute lymphocyte count <4000/microL) in the setting of a circulating LGL count of less than 500/microL.
- Partial response — A hematologic partial response is defined as an improvement in blood counts that does not meet criteria for complete remission (eg, an absolute neutrophil count >500/microL or decreasing transfusion requirements).
- Treatment failure — Treatment failure is defined as an inability to achieve an at least partial response after four months of therapy.
- Progressive disease — Progressive disease is defined as a worsening of cytopenias, hepatomegaly, or splenomegaly

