3. PARTICIPANT SELECTION

3.1 Eligibility Criteria

Participants must meet the following criteria on screening examination to be eligible to participate in the study:

Subjects with CLL/SLL:

3.1.1 Subjects must be diagnosed with CLL / SLL (chronic lymphocytic leukemia / small lymphocytic lymphoma) based on the standard histologic and immunophenotypic criteria described in the WHO classification of lymphoid malignancies, including immunophenotypic confirmation that the tumor cells co-express B cell antigens CD19 / 20 and CD5. Mantle cell lymphoma should be excluded based on positive staining of the tumor cells for CD23, or the absence of staining of the tumor cells for cyclin D1 or the absence of t(11;14). This diagnosis should be confirmed at a Dana-Farber Harvard Cancer Center institution (DFCI, BWH, MGH, BIDMC) within approximately one month after the subject is registered. Any question on histology confirmation should be brought to the attention of the Principal Investigator.

3.1.2 Participants must have measurable disease, defined as lymphocytosis \geq 5,000 / ul, or at least one palpable or CT measurable lesion $>$ approximately 1.5 cm, or bone marrow involvement $>$ approximately 30%.

3.1.3 Subjects must have relapsed after at least one prior purine analogue-containing regimen (fludarabine, cladribine or pentostatin), OR at least two non-purine analogue containing regimens.

Subjects with T-LGL:

T-LGL judged by the investigator to require therapy based upon:

- 1) Severe neutropenia (absolute neutrophil count $<$ 500/microL)
- 2) Moderate neutropenia (absolute neutrophil count $<$ 1000/microL) with recurrent infections
- 3) Symptomatic or transfusion dependent anemia
- 4) Severe thrombocytopenia ($<$ 50,000/microL)
- 5) Hepatic infiltration resulting in abnormal liver function tests
- 6) Symptomatic splenomegaly

Patients with previously untreated or relapsed/refractory disease will be eligible

All Subjects:

3.1.4 Age \geq 18 years.

3.1.5 Life expectancy of greater than 3 months.

3.1.6 ECOG performance status \leq 2 (Karnofsky \geq 60%, see Appendix B).

3.1.7 Participants must have normal organ function as defined below:

- total bilirubin $\leq 1.5X$ institutional ULN unless due to indirect hyperbilirubinemia related to Gilbert's syndrome or hemolysis, or to disease infiltration
- AST (SGOT)/ALT (SGPT) $\leq 5 X$ institutional upper limit of normal
- creatinine $\leq 2X$ institutional ULN

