5.4 General Concomitant Medication and Supportive Care Guidelines

Patients will receive the following additional supportive care medications:

- Allopurinol 300 mg po QD day 1-10 after initiation of study therapy. This would be considered standard of care, unless the subject has an allergy. Subjects with T-LGL are not required to receive allopurinol.
- Anti-emetics may be prescribed as needed; no specific premedication is required or suggested.
- Subjects who have been taking trimethoprim-sulfamethoxazole for PCP prophylaxis should be assessed for their real risk of PCP. Due to an increased risk of hypersensitivity reactions and/or myelosuppression when given together with

pyrimethamine, this medication should be discontinued if possible or changed to atovaquone or other equivalent PCP prophylaxis during the time on study therapy.

- Subjects receiving acyclovir or equivalent prophylaxis should continue these medications. Consideration should be given to initiating acyclovir prophylaxis at 400 mg po TID (or equivalent) for those patients not yet receiving it.
- Lorazepam given concurrently with pyrimethamine has been associated with an increased risk of transaminitis. If substitution with another benzodiazepine or other medication is possible, then that is preferred; otherwise close monitoring is appropriate.
- All patients requiring transfusions should receive irradiated, leukopore filtered blood products.
- Subjects may receive neupogen, pegfilgrastim, erythropoietin or related growth factors at the discretion of the treating physician. Subjects in whom study therapy has been held due to myelosuppression may be given a short course of leucovorin 10 mg po QD, at the discretion of the treating physician in consultation with the Principal Investigator.
- Because there is a potential for interaction of pyrimethamine with other concomitantly administered drugs, especially sulfonamides or myelosuppressive drugs, the case report form must capture the concurrent use of all other drugs, over-the-counter medications, or alternative therapies.

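### A T-LGL partial response needs no repeat count and may rest on growth-factor- or transfusion-supported counts, yet it counts in full in the pooled response rate

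*Combined protocol and SAP*

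**What the plan says.** **T-LGL criteria (Section 10).** PR is worded "A hematologic partial response is defined as an improvement in blood counts that does not meet criteria for complete remission", followed by examples only: "eg, an absolute neutrophil count >500/microL or decreasing transfusion requirements". CR begins "A hematologic complete response is defined as the complete normalization of blood counts", with thresholds for hemoglobin, platelets, ANC and lymphocytes, and also requires circulating LGL below 500/microL. Failure is defined by time: "Treatment failure is defined as an inability to achieve an at least partial response after four months of therapy". Neither PR nor CR states a repeat count, a duration, or how to treat a supported count.

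**Timing (Section 10).** Response is assessed at the end of the 28-day first cycle, "then at the conclusion of three cycles (three months), and then every three months thereafter".

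**Entry and support.** Section 3.1 lists ANC below 500/microL as one ground for treating T-LGL. Section 5.4 states: "Subjects may receive neupogen, pegfilgrastim, erythropoietin or related growth factors at the discretion of the treating physician". Section 6.3.1 allows growth factors throughout therapy when the starting ANC is below 1000, or is above 1000 only with growth factors.

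**CLL/SLL (Section 10.2).** PR needs two Group A criteria plus one from Group B, must last at least two months and must be confirmed at restaging. CR hemoglobin must be free of transfusion and erythropoietin. The Group B values for PR carry no such condition.

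**Decision rule (Section 14.2.2).** One response rate covers both diseases. The trial stops with 0 or 1 responses in the first 10 patients, and fewer than 5 in 26 is not promising.

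**The concern.** The neutrophil example of a T-LGL PR sits at the same cut-point as a T-LGL entry criterion. A patient selected for a count below 500 can exceed it at day 28 through ordinary fluctuation or because a growth factor was started. As written, either fits the PR definition. Transfused platelets or hemoglobin could likewise pass as improved counts.

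Each such PR is half of the two responses needed to pass stage 1 and a fifth of the five needed for success. With a single arm, nothing in the data separates a drug effect from a support effect or from one high count after entry at a low one. The pooled endpoint also mixes two standards: a durable, restaged PR in CLL/SLL and a possibly momentary one in T-LGL.

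**Working it through.** **1. Reproduce the design (Section 14.2.2).** Inputs: n1 = 10, continue with 2 or more responses; n = 26, promising with 5 or more; null 10%, target 35%. With X1 ~ Bin(10, p) and X2 ~ Bin(16, p),

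P(promising) = sum over x = 2 to 10 of P(X1 = x) × P(X2 ≥ 5 − x).

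At p = 0.10:

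| x | P(X1 = x) | P(X2 ≥ 5 − x) | Product |
|---|---|---|---|
| 2 | 0.1937 | 0.2108 | 0.0408 |
| 3 | 0.0574 | 0.4853 | 0.0279 |
| 4 | 0.0112 | 0.8147 | 0.0091 |
| 5 or more | 0.0016 | 1 | 0.0016 |

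The sum is 0.0794, within the stated 10%. The probability of stopping at stage 1 is 0.7361, which matches the plan's 0.736. At p = 0.35, power is 0.9034. The design reproduces.

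**2. Add T-LGL patients scored without a drug effect.** Let k1 and k2 be the T-LGL patients in stages 1 and 2, q their non-drug PR rate and p the CLL/SLL rate. Then X1 = Bin(10 − k1, p) + Bin(k1, q), X2 = Bin(16 − k2, p) + Bin(k2, q), and the same sum applies. The documents do not give k1, k2 or q, so all are assumed. Each range runs over every stage split. Its low end has all T-LGL patients in stage 2 and its high end has all in stage 1.

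| T-LGL patients | p = 0.10, q = 0.2 | p = 0.10, q = 0.3 | p = 0.10, q = 0.5 | p = 0.05, q = 0.3 |
|---|---|---|---|---|
| 1 | 0.087-0.094 | 0.094-0.108 | 0.109-0.137 | 0.009-0.012 |
| 3 | 0.102-0.126 | 0.124-0.180 | 0.169-0.304 | 0.020-0.039 |
| 5 | 0.117-0.163 | 0.153-0.264 | 0.214-0.497 | 0.033-0.090 |

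**3. Find the q at which the 10% limit is reached.**

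- CLL/SLL at 10%: q = 0.242-0.379 with one T-LGL patient, 0.146-0.192 with three, 0.127-0.155 with five.
- CLL/SLL at 5%: never with one. With three or five it is never reached if all are in stage 2; otherwise q must be at least 0.539 (three) or 0.317 (five).

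**The case against.** **CR is better protected.** It needs circulating LGL below 500/microL and normal values in all lines together, and the documents give no reason why growth factors or transfusion would clear LGL. A reader might infer that CR is as exposed as PR; the text does not support that. The marrow check of CR in footnote 7 of the Study Calendar does not help PR, however. Under Section 14.6.2 a CR without marrow becomes a PR, which still counts.

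**CLL/SLL is not free of the support gap.** Its Group B values for PR have no support exclusion, so silence on support is not peculiar to T-LGL. This stands. The remaining difference is that CLL PR also needs two Group A criteria and the two-month hold, so a supported neutrophil count alone cannot produce it.

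**The Section 10.2 hold might be meant for both diseases.** The table is headed for hematologic tumors in general, but its parameters are CLL-specific (B-lymphoid nodules, declines attributed to CLL), and T-LGL has its own list. If the hold was meant to apply, the text should say so.

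**The T-LGL criteria are cited from a publication.** That source may contain confirmation or support rules. It is not available here, and no such rule appears in the protocol wording.

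**The data to detect the problem exist.** Blood counts are frequent, and Section 5.4 says "the case report form must capture the concurrent use of all other drugs". A careful analyst could spot transient or supported responses, but no rule requires it.

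**The bias may be small or offset.** Neutropenic LGL patients may stay on drug without support (Section 6.3.1). The loose T-LGL definition of progression and drug myelosuppression both push the other way. This also stands.

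**Conclusion.** The point holds for PR: applied as written, the definition can score a non-drug effect as a full response in the primary endpoint. That is more than missing detail, and it should be fixed.

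A reader might infer that the trial's type I error is above 10%. The documents do not show this. Inflation appears with CLL/SLL at the full null rate, a sufficient non-drug T-LGL rate and, for any sizeable effect, several T-LGL patients. With one T-LGL patient and q = 0.3 the result is close to the nominal limit (0.094-0.108). With CLL/SLL at 5% and q = 0.3 it is never passed in the cases shown. The T-LGL number, stage split and q are all assumptions. The wording gap is certain; how often it would matter is not known.

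**What to change.** Change the endpoint scoring in Section 10 only, and leave supportive care as it is.

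1. Count a T-LGL PR in the response rate only if the improvement from baseline is still present at the next formal response assessment, within the protocol's visit windows: end of cycle 1 then end of cycle 3, or the following scheduled assessment. Tie the repeat to the visit, not to a fixed two months. The cycle 1 to cycle 3 interval is 2 × 28 = 56 days, and ±3 days at each end allows 50. State that the four-month failure rule refers to first meeting PR.
2. Do not score a count as improved if it is measured under growth-factor or transfusion support that is new or increased since baseline. Compare patients on constant support with their supported baseline. Judge reduced transfusion need over equal prespecified windows before and during treatment, with the sponsor setting the window.
3. Apply the same scoring to the six Phase I patients counted in Phase II.

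**Cost.** Endpoint wording and a CRF check; transfusion dates, including the pre-treatment window, may need one field. The CLL hold already imposes a wait before responses can be counted at stage 1, although a T-LGL PR first seen at the end of cycle 3 would wait three months for its repeat.

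The observed response rate will be lower, and a true responder on new support cannot be scored until support stops. If the true rate is 35% but the scored T-LGL rate falls to an assumed 20%, power drops from 0.903 to 0.888-0.902 with one T-LGL patient, 0.848-0.897 with three and about 0.798-0.891 with five. The fix sets no minimum size of improvement, so a small, repeated, unsupported rise would still count.
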